### Exposure during lactation

Situations of exposure during lactation should be reported, independently of presence of a concomitant AE.

A report of exposure during lactation does not have to be performed when a Pfizer product specifically indicated for use in a breastfeeding woman (for example, vitamins) is administered in agreement with the MA.

However, if the infant presents an AE associated with administration of such a medicinal product, the AE must be reported with exposure during lactation.

### Medicinal product error

A medicinal product error means any unintentional error in prescription, in dispensing or administration of a medicinal product, which can cause or lead to inappropriate use of a medicinal product or harm for the patient, even though it occurs under control of a health care professional, of the patient or the consumer. Such events can be related to professional practice, to products, to procedures and to systems in particular: in prescribing; transmission of an order; product information; packaging and nomenclature of a product; composition; dispensing; distribution; administration; training in product; monitoring and use.

Medicinal product errors include the following:

- “Almost” adverse events, involving a patient directly or not (for example, inadvertent or erroneous administration, which is the accidental use of a product off-label or prescription by a health care professional or a patient/consumer);
- Confusion concerning the product name (for example, tradename, brand name).

The participating doctor must report the following medicinal product errors to Pfizer, independently of presence of a concomitant AE/SAE:

- Medicinal product errors involving exposure of a patient to the product, whether the medicinal product is accompanied by an adverse event or not.
- Medicinal product errors not involving a patient directly (for example, potential or almost accidental medicinal product errors). Whenever a medicinal product error does not involve exposure of a patient to the product, the following minimum criteria comprise a case of a medicinal product error:
  - An identifiable notifying party;
  - A suspect product;
  - A medicinal product error.

### Overdose, Misuse, Extravasation

PFIZER CONFIDENTIAL

CT24WI-GL02-RF01.1.0 Model of non-interventional study protocol for study on collection of principal data

15/08/2018

Page 54 of 79

Cases of overdose, misuse and extravasation associated with use of a Pfizer product must be reported to Pfizer by the participating doctor, independently of the presence of an associated AE/SAE.

#### Lack of efficacy

Cases of lack of efficacy of a Pfizer product must be reported to Pfizer by the participating doctor, independently of the existence of an associated AE/SAE or of the indication of the Pfizer product.

#### Occupational exposure

Cases of occupational exposure to a Pfizer product must be reported to Pfizer by the participating doctor independently of the presence of an associated AE/SAE.

## **12. PLANS FOR DISCLOSURE AND COMMUNICATION OF RESULTS OF STUDY**

### **12.1. Confidentiality**

All data on patients participating in the study must be collated with appropriate precautions to ensure confidentiality of such data, according to applicable laws and regulations on protection of personal data (French law 78-17 of 6 January 1978, modified by law 2004-801 of 6 August 2004).

In all presentations of study results, at meetings or in publications, the identity of patients will remain confidential and all data will be issued anonymously.

### **12.2. Ownership of data**

Pfizer will retain ownership of all forms of case reports, data analyses and reports which result from the study.

### **12.3. Communications and publications**

All information obtained from this study will be considered confidential, up until analysis and final review by Pfizer and by members of the scientific committee have been completed.

Results of the study can be edited or presented by members of the scientific committee after the review and agreement of Pfizer, and such as confidential information or industrial property are not disclosed. Before publication of presentation, a copy of the final text must be sent by the member(s) of the scientific committee to Pfizer, for comment. Such comments

will seek to ensure the scientific content of publications and/or of proposed presentations and to ensure that the data and material relating to Pfizer products and activities received an equitable, precise and reasonable presentation.

#### **12.4. Communication of problems**

In the eventual case of prohibition or a restriction imposed (for example, suspension of the clinical trial) by responsible competent authority in whatever region of the world, or if the participating doctor becomes aware of new information which may affect the evaluation of the benefits and risks of a Pfizer product, Pfizer must immediately be informed of it.

Furthermore, the participating doctor will immediately inform Pfizer of all urgent measures of safety taken by the participating doctor in order to protect patients in the study against any immediate hazard, and of all serious violations of the NI study protocol for which the participating has become aware.

**ANNEX 1. LIST OF INDEPENDENT DOCUMENTS**

Number	Document reference number	Date	Title
1	3.0	15-FEB-2019	Information leaflet and patient consent
2	2.0	15-FEB-2019	Case report forms

## ANNEX 2. ENCePP CHECKLIST FOR STUDY PROTOCOLS

Doc.Ref. EMA/540136/2009

### ENCePP Checklist for Study Protocols (Revision 2, amended)

Adopted by the ENCePP Steering Group on 14/01/2013

The [European Network of Centres for Pharmacoepidemiology and Pharmacovigilance \(ENCePP\)](#) welcomes innovative designs and new methods of research. This Checklist has been developed by ENCePP to stimulate consideration of important principles when designing and writing a pharmaco-epidemiological or pharmacovigilance study protocol. The Checklist is intended to promote the quality of such studies, not their uniformity. The user is also referred to the [ENCePP Guide on Methodological Standards in Pharmacoepidemiology](#) which reviews and gives direct electronic access to guidance for research in pharmacoepidemiology and pharmacovigilance.

For each question of the Checklist, the investigator should indicate whether or not it has been addressed in the study protocol. If the answer is "Yes", the page number(s) of the protocol where this issue has been discussed should be specified. It is possible that some questions do not apply to a particular study (for example in the case of an innovative study design). In this case, the answer 'N/A' (Not Applicable) can be checked and the "Comments" field included for each section should be used to explain why. The "Comments" field can also be used to elaborate on a "No" answer.

This Checklist should be included as an Annex by marketing authorization holders when submitting the protocol of a non-interventional post-authorization safety study (PASS) to a regulatory authority (see the [Guidance on the format and content of the protocol of non-interventional post-authorization safety studies](#)). Note, the Checklist is a supporting document and does not replace the format of the protocol for PASS as recommended in the Guidance and Module VIII of the Good pharmacovigilance practices (GVP).

**Study title:**

**Study reference number:**

Section 1: Milestones	Yes	No	N/A	Page Number(s)
1.1 Does the protocol specify timelines for 1.1.1 Start of data collection 				

 Date from which information on the first study is first recorded in the study dataset or, in the case of secondary use of data, the date from which data extraction starts.

Section 1: Milestones	Yes	No	N/A	Page Number(s)
1.1.2 End of data collection 				
1.1.3 Study progress report(s)				
1.1.4 Interim progress report(s)				
1.1.5 Registration in the EU PAS register				
1.1.6 Final report of study results.				

Comments:

--

Section 2: Research question	Yes	No	N/A	Page Number(s)
2.1 Does the formulation of the research question and objectives clearly explain:				
2.1.1 Why the study is conducted? (e.g. to address an important public health concern, a risk identified in the risk management plan, an emerging safety issue)				
2.1.2 The objective(s) of the study?				
2.1.3 The target population? (i.e. population or subgroup to whom the study results are intended to be generalized)				
2.1.4 Which formal hypothesis(-es) is (are) to be tested?				
2.1.5 If applicable, that there is no a priori hypothesis?				

Comments:

--

Section 3: Study design	Yes	No	N/A	Page Number(s)
3.1 Is the study design described? (e.g. cohort, case-control, randomized controlled trial, new or alternative design)				
3.2 Does the protocol specify the primary and secondary (if applicable) endpoint(s) to be investigated?				
3.3 Does the protocol describe the measure(s) of effect? (e.g. relative risk, odds ratio, deaths per 1000 person-years, absolute risk, excess risk, incidence rate ratio, hazard ratio, number needed to harm (NNH) per year)				

Comments:

--

 Date from which the analytical dataset is completely available.

Section 4: Source and study populations	Yes	No	N/A	Page Number(s)
4.1 Is the source population described?				
4.2 Is the planned study population defined in terms of:				
4.2.1 Study time period?				
4.2.2 Age and sex?				
4.2.3 Country of origin?				
4.2.4 Disease/indication?				
4.2.5 Co-morbidity?				
4.2.6 Seasonality?				
4.3 Does the protocol define how the study population will be sampled from the source population? (e.g. event or inclusion/exclusion criteria)				

Comments:

--

Section 5: Exposure definition and measurement	Yes	No	N/A	Page Number(s)
5.1 Does the protocol describe how exposure is defined and measured? (e.g. operational details for defining and categorizing exposure)				
5.2 Does the protocol discuss the validity of exposure measurement? (e.g. precision, accuracy, prospective ascertainment, exposure information recorded before the outcome occurred, use of validation sub-study)				
5.3 Is exposure classified according to time windows? (e.g. current user, former user, non-use)				
5.4 Is exposure classified based on biological mechanism of action and taking into account the pharmacokinetics and pharmacodynamics of the drug?				
5.5 Does the protocol specify whether a dose-dependent or duration-dependent response is measured?				

Comments:

--

Section 6: Endpoint definition and measurement	Yes	No	N/A	Page Number(s)
6.1 Does the protocol describe how the endpoints are defined and measured?				

Section 6: Endpoint definition and measurement	Yes	No	N/A	Page Number(s)
6.2 Does the protocol discuss the validity of endpoint measurement? (e.g. precision, accuracy, sensitivity, specificity, positive predictive value, prospective or retrospective ascertainment, use of validation sub-study)				

Comments:

--

Section 7: Confounders and effect modifiers	Yes	No	N/A	Page Number(s)
7.1 Does the protocol address known confounders? (e.g. collection of data on known confounders, methods of controlling for known confounders)				
7.2 Does the protocol address known effect modifiers? (e.g. collection of data on known effect modifiers, anticipated direction of effect)				

Comments:

--

Section 8: Data sources	Yes	No	N/A	Page Number(s)
8.1 Does the protocol describe the data source(s) used in the study for the ascertainment of: 8.1.1 Exposure? (e.g. pharmacy dispensing, general practice prescribing, claims data, self-report, face-to-face interview, etc.) 8.1.2 Endpoints? (e.g. clinical records, laboratory markers or values, claims data, self-report, patient interview including scales and questionnaires, vital statistics, etc.) 8.1.3 Covariates?				
8.2 Does the protocol describe the information available from the data source(s) on: 8.2.1 Exposure? (e.g. date of dispensing, drug quantity, dose, number of days of supply prescription, daily dosage, prescriber) 8.2.2 Endpoints? (e.g. date of occurrence, multiple event, severity measures related to event) 8.2.3 Covariates? (e.g. age, sex, clinical and drug use history, co-morbidity, co-medications, life style, etc.)				
8.3 Is a coding system described for: 8.3.1 Diseases? (e.g. International Classification of Diseases (ICD)-10) 8.3.2 Endpoints? (e.g. Medical Dictionary for Regulatory Activities (MedDRA) for adverse events) 8.3.3 Exposure? (e.g. WHO Drug Dictionary, Anatomical Therapeutic Chemical (ATC) Classification System)				

PFIZER CONFIDENTIAL

CT24WI-GL02-RF01.1.0 Model of non-interventional study protocol for study on collection of principal data

15/08/2018

Page 64 of 79

Section 8: Data sources	Yes	No	N/A	Page Number(s)
8.4 Is the linkage method between data sources described? (e.g. based on a unique identifier or other)				

Comments:

--

Section 9: Study size and power	Yes	No	N/A	Page Number(s)
9.1 Is sample size and/or statistical power calculated?				

Comments:

--

Section 10: Analysis plan	Yes	No	N/A	Page Number(s)
10.1 Does the plan include measurement of excess risks?				
10.2 Is the choice of statistical techniques described?				
10.3 Are descriptive analyses included?				
10.4 Are stratified analyses included?				
10.5 Does the plan describe methods for adjusting for confounding?				
10.6 Does the plan describe methods addressing effect modification?				

Comments:

--

Section 11: Data management and quality control	Yes	No	N/A	Page Number(s)
11.1 Is information provided on the management of missing data?				
11.2 Does the protocol provide information on data storage? (e.g. software and IT environment, database maintenance and anti-fraud protection, archiving)				
11.3 Are methods of quality assurance described?				
11.4 Does the protocol describe possible quality issues related to the data source(s)?				
11.5 Is there a system in place for independent				

PFIZER CONFIDENTIAL

CT24WI-GL02-RF01.1.0 Model of non-interventional study protocol for study on collection of principal data

15/08/2018

Page 65 of 79

Section 11: Data management and quality control	Yes	No	N/A	Page Number(s)
review of study results?				

Comments:

--

Section 12: Limitations	Yes	No	N/A	Page Number(s)
12.1 Does the protocol discuss: 12.1.1 Selection biases? 12.1.2 Information biases? (e.g. anticipated direction and magnitude of such biases, validation sub-study, use of validation and external data, analytical methods)				
12.2 Does the protocol discuss study feasibility? (e.g. sample size, anticipated exposure, duration of follow-up in a cohort study, patient recruitment)				
12.3 Does the protocol address other limitations?				

Comments:

--

Section 13: Ethical issues	Yes	No	N/A	Page Number(s)
13.1 Have requirements of Ethics Committee/Institutional Review Board approval been described?				
13.2 Has any outcome of an ethical review procedure been addressed?				
13.3 Have data protection requirements been described?				

Comments:

--

Section 14: Amendments and deviations	Yes	No	N/A	Page Number(s)
14.1 Does the protocol include a section to document future amendments and deviations?				

Comments:

--

Section 15: Plans for communication of study results	Yes	No	N/A	Page Number(s)

Section 15: Plans for communication of study results	Yes	No	N/A	Page Number(s)
15.1 Are plans described for communicating study results (e.g. to regulatory authorities)?				
15.2 Are plans described for disseminating study results externally, including publication?				

Comments:

--

Name of the main author of the protocol: \_\_\_\_\_

Date:    /    /

Signature: \_\_\_\_\_

## ANNEX 3. ADDITIONAL INFORMATION

### Annex 3.1: ECOG Performance Status

#### ECOG Performance Status

---

*These scales and criteria are used by doctors and researchers to assess how a patient's disease is progressing, to assess how the disease affects the daily living abilities of the patient, and determine appropriate treatment and prognosis. They are included here for health care professionals to access.*

---

ECOG PERFORMANCE STATUS*	
Grade	ECOG
0	Fully active, able to carry on all pre-disease performance without restriction
1	Restricted in physically strenuous activity but ambulatory and able to carry out work of a light or sedentary nature, e.g., light house work, office work
2	Ambulatory and capable of all self-care but unable to carry out any work activities. Up and about more than 50% of waking hours
3	Capable of only limited self-care, confined to bed or chair more than 50% of waking hours
4	Completely disabled. Cannot carry on any self-care. Totally confined to bed or chair
5	Dead

\* As published in Am. J. Clin. Oncol.: Oken, M.M., Creech, R.H., Tormey, D.C., Horton, J., Davis, T.E., McFadden, E.T., Carbone, P.P.: Toxicity And Response Criteria Of The Eastern Cooperative Oncology Group. Am J Clin Oncol 5:649-655, 1982.

The ECOG Performance Status is in the public domain therefore available for public use. To duplicate the scale, please cite the reference above and credit the Eastern Cooperative Oncology Group, Robert Comis M.D., Group Chair.

### Annex 3.2 SOKAL Index

The SOKAL index is calculated based on the following parameters before start of any treatment:

- Age (years)
- Spleen size (cm under the costal border)
- Platelet count before and at start of treatment ( $10^9/l$ )
- Percent of blast in peripheral blood (%)

The SOKAL index is calculated according to the following formula:

$$\exp [0.116 (\text{age}-43.4)] + 0.0345(\text{spleen size}-7.51) + 0.188[(\text{platelets}/700)^2 - 0.563] + 0.0887(\% \text{ blasts} - 2.1)$$

After calculation of the SOKAL index, patients will be evaluated as follows:

- At low risk if SOKAL Score is less than 0.8
- At intermediate risk if SOKAL Score is between 0.8 - 1.2
- At high risk if SOKAL Score is greater than 1.2

*ref: Sokal JE, Cox EB, Baccarani M, Tura S, Gomez GA, Robertson JE, et al. Prognostic discrimination in "good-risk" chronic granulocytic leukemia. Blood 1984;63:789-99*

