## 7. RATIONALE AND GENERAL CONSIDERATIONS

### 7.1. Chronic myeloid leukemia

Chronic myeloid leukemia (CML) is a malignant hematological disease which belongs to the group of myeloproliferative syndromes (or myeloproliferative neoplasia according to WHO classification 2008 [1]). This hematologic disease is a rare disease, with 600 to 700 new cases per year (the incidence in France is estimated at 1 or 2 cases per 100,000 persons, and increasing with age) [2], accounting for 15% to 20% of all cases of leukemia [3]. Mean age at time of diagnosis is 54 years and the disease affects 1.4 males vs. 1 female patient. The prevalence, on the order of 6000 to 7000 patients in France, is on the increase because of a frank decrease in mortality rate, at least during the first 6 years after the diagnosis [2].

CML results from a specific chromosomal anomaly which occurs in hematopoietic stem cells, although the principal cause of this anomaly is not yet understood. It is characterized by the presence of a chromosomal marker in hematopoietic cells, the Philadelphia chromosome (Ph1 chromosome), which can be detected in 95% of patients with CML [4]. The chimeric protein BCR-ABL (Breakpoint Cluster Region – Abelson), resulting from

translocation t(9; 22) at the origin of the Philadelphia chromosome positive (Ph+), has a high tyrosine kinase activity responsible for leukemic transformation by resulting in excessive and persistent production of white blood cells.

The disease, referred to as chronic, develops gradually and evolves slowly in three successive phases, becoming increasingly resistant to treatments with progression of disease: chronic phase (CP CML), accelerated phase (AP CML) and blast phase (blast crisis) (BP CML). The majority of patients are diagnosed during the chronic phase. Without treatment, patients in chronic phase CML will progress to the accelerated phase in 4 to 6 years. Patients diagnosed during the accelerated phase have a life expectancy estimated at less than 12 months in the absence of treatment. Following the blast phase, patients live on average 2 to 4 months if they are not treated [4].

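### The Sokal formula printed in Annex 3.2 is incompatible with the annex's own risk bands: every patient aged 49 or older scores as high risk whatever the spleen, platelets or blasts

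*Protocol*

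**What the plan says.** Annex 3.2 of the protocol builds the Sokal index from four pre-treatment inputs: age, spleen size, platelet count and percentage of blasts in peripheral blood. Spleen is recorded as "Spleen size (cm under the costal border"), so it cannot be below zero.

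The printed formula starts "\exp [0.116 (\text{age}-43.4)] + 0.0345(\text{spleen size}-7.51") and then adds "0.188[(\text{platelets}/700)^2 - 0.563"] and "0.0887(\% \text{ blasts} - 2.1"). The exponential covers the age term only.

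The annex then gives an operative rule: "After calculation of the SOKAL index, patients will be evaluated as follows". The bands are "At low risk if SOKAL Score is less than 0.8", intermediate from 0.8 to 1.2, and "At high risk if SOKAL Score is greater than 1.2". A published source for the index is cited at the foot of the annex.

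Section 7.1 supplies the one age figure needed for context: "Mean age at time of diagnosis is 54 years".

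**The concern.** A four-input index with three risk groups should let all four inputs move a typical patient between groups. As printed, the age term grows exponentially at 0.116 per year, while the other three terms are added on a linear scale and have small floors. Over most of the age range seen in this disease, age then swamps the rest and the bands stop discriminating. At the young end, the sum can fall below zero, although the lowest band gives no sign that negative scores were intended.

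What is at stake is any risk classification programmed from this annex. A Sokal class derived from it would put everyone from age 49 upward into one group, and would misstate case mix if used to describe the cohort or to adjust a model.

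**Working it through.** **Inputs**, all from Annex 3.2 unless stated: age coefficient 0.116, centred at 43.4; spleen coefficient 0.0345, centred at 7.51 cm; platelet coefficient 0.188 on (platelets/700)² − 0.563; blast coefficient 0.0887, centred at 2.1%; cut-offs 0.8 and 1.2. Mean age at diagnosis is 54 (section 7.1). The protocol reports no worked Sokal value, so there is no figure of its own to reproduce first.

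**Step 1. Floor of the three non-age terms** (spleen 0 cm, platelets 0, blasts 0%):

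- spleen: −0.0345 × 7.51 = −0.259
- platelets: −0.188 × 0.563 = −0.106
- blasts: −0.0887 × 2.1 = −0.186
- sum: −0.551

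**Step 2. Age at which high risk is forced.** A score above 1.2 is certain once exp[0.116(age − 43.4)] > 1.2 + 0.551 = 1.751, that is, age > 43.4 + ln(1.751)/0.116 = 48.2. In whole years, age 49 is the first.

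| Age | Age term | Lowest possible score | Class at that minimum |
|---|---|---|---|
| 48 | 1.705 | 1.154 | intermediate |
| 49 | 1.915 | 1.364 | high |
| 54 | 3.420 | 2.869 | high |
| 70 | 21.881 | 21.329 | high |

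At age 54 the minimum is more than twice the high-risk cut-off. The floor uses a platelet count of zero, which is more generous than any real patient. With platelets of 300, spleen 0 and blasts 0%, the score at 54 is 3.420 − 0.517 = 2.90.

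**Step 3. Negative scores.** With spleen 0 cm and blasts 0%, the score is below zero when the age term is smaller than the amount that the other terms subtract. That amount depends on platelets:

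| Platelets (10⁹/l) | Non-age sum | Score negative below age |
|---|---|---|
| 0 (limit) | −0.551 | 38.3 |
| 300 | −0.517 | 37.7 |
| 700 | −0.363 | 34.7 |
| 1000 | −0.168 | 28.0 |

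For example, at age 30 with platelets of 300 the score is 0.211 − 0.517 = −0.31.

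**Step 4. Would a misplaced bracket explain it?** Put the whole sum inside the exponential and keep 0.116. The minimum score is then exp[0.116(age − 43.4) − 0.551], which exceeds 1.2 when age > 43.4 + (ln 1.2 + 0.551)/0.116 = 43.4 + (0.182 + 0.551)/0.116 = 49.7. Everyone aged 50 or older is still high risk, with a minimum of 1.97 at age 54. Negative scores disappear, but the main fault remains.

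**Step 5. Illustration only.** Suppose the age coefficient were ten times smaller (0.0116) and all terms sat inside the exponential. Neither is given in the protocol; both are assumptions to verify. At age 54 with spleen 0, platelets 300 and blasts 0%, the score is exp(0.0116 × 10.6 − 0.517) = exp(−0.394) = 0.67, which is low risk and of a size that fits the printed bands.

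**The case against.** **The index is not used.** It appears only in Annex 3.2. The objectives (section 8), the variables table (section 9.3) and the analyses (section 9.7) do not name it, and spleen size, a required input, is not a listed variable. Descriptions and the mixed models are organised by disease phase and treatment line. This stands, and it limits the consequence. A reader might infer that the error invalidates analyses of adverse events, response or survival by risk group, but no such analysis is planned. The logistic models in section 9.7.1 are adjusted for potential confounders without naming Sokal.

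**Age does not settle the class at every age.** A reader might infer that the printed score is simply an age split at about 48. That is too strong. At age 40 the formula gives 0.16 (low) with spleen 0, platelets 300 and blasts 0%, but 1.47 (high) with spleen 15 cm, platelets 1000 and blasts 5%. Age overrides the rest only from 49 upward.

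**The number misclassified is unknown.** It is tempting to say that most patients would be mislabelled. The protocol gives a mean age at diagnosis but no distribution, and some patients aged 49 or older may truly be high risk. What can be said is that all of them would be labelled high risk.

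**The text was extracted from a PDF.** A moved bracket would not rescue the formula (step 4). A lost zero in the age coefficient would: with the printed brackets and 0.0116, the minimum at age 54 is 1.131 − 0.551 = 0.58. Nothing in the annex points to such a loss, and the neighbouring coefficients 0.0345 and 0.0887 kept their leading zeros. The possibility remains, and the sponsor can settle it by looking at one line of the original page.

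**Conclusion.** The point holds as a contained error in the annex. The printed formula and the 0.8 and 1.2 bands beneath it cannot both be right. From age 49 the class is high risk regardless of three of the four inputs. At 38 or younger, some patients with no palpable spleen, no blasts and low or normal platelets score below zero, the exact age depending on the platelet count. This follows from the annex's own figures and needs no outside source. It rests on the formula having been read correctly from the page.

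The harm is conditional: it reaches any baseline risk description or model adjustment that uses a Sokal class derived from this annex. The primary objectives and the sample size do not depend on it.

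A reader might infer that the documents show the correct formula to have all four terms inside the exponential and a coefficient of 0.0116. They do not. They show only that the printed version fails and that moving the bracket alone does not repair it.

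**What to change.** Check both the age coefficient and the extent of the exponential against the reference cited in Annex 3.2, and correct the printed line. Check any eCRF or program derivation of the score against the corrected version, and recompute any scores already derived. If no derivation exists, correcting the annex is enough.

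The cost is one line in the annex, plus a check of the derivation code if there is any. No new data collection follows from the correction itself.
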